**Study Procedures Table for Control group**

	Screening and Consent	Baseline (Day 0)	60-day visit	120-day visit	180-day visit (final visit)
Signed informed consent	X	X			
Medical History/questionnaire		X	X	X	X
stool collection for bacterial and sIgA analysis		X	X	X	X

I. Data Collection

Demographic and clinical information will be collected whenever clinical data are available via uniform baseline and follow up clinical data extraction forms to ensure accuracy and consistency. The essential demographic information includes age at diagnosis, gender, race and ethnicity, birth history and past medical history. The clinical information includes bowel length, dates and type of surgeries, nutrition data (formula type, amount, weaning foods, parenteral nutrition type and amount), infection type (genus, species and susceptibility to antibacterials) date infection is diagnosed) hospital admissions and hospital length of stay.

J. Compensation

Participants will receive \$10 for every stool collected for analysis during study participation. Subjects will receive study medication, clinical supplies, and laboratory evaluations related to the study free of charge.

## **X. Assessment of Efficacy**

**Hypothesis 1:** Enteral GLN supplementation in infants with SBS after massive bowel resection for NEC will decrease BSI, and thereby decrease systemic proinflammatory cytokine concentrations.

**Specific Aim 1:** To perform a double-blind, randomized, placebo controlled, 6-months pilot study of enteral GLN (0.6g/kg) vs. isocaloric, isonitrogenous alanine (placebo) treatment in PN-dependent SBS children due to NEC to evaluate the efficacy of GLN to decrease: a) BSI (primary endpoint) and b) serial serum concentrations of TNF- $\alpha$ , IL-1 $\beta$ , IL-6 and IL-8 (secondary endpoint). **The primary outcome is the incidence of BSI during the 6 months on GLN supplementation.** BSI is defined as laboratory-confirmed, culture-proven bloodstream infections that meet the Centers for Disease Control and Prevention (CDC) definition. This allows for the distinction between catheter related-BSI and other causes of BSI.

**Secondary outcomes:** 1) Plasma proinflammatory cytokine levels (TNF- $\alpha$ , IL-1 $\beta$ , IL-6, IL-8); 2) readmissions and hospital length of stay; 3) proportion of nutrition delivered enterally versus parenterally; 4) stool sIgA levels; 5) Plasma glutamine.

**Expected results:** We expect that the SBS children on enteral GLN supplementation will have significantly fewer BSI and greater decline in blood cytokine levels during the period of therapy.

**Hypothesis 2:** Enteral GLN supplementation will improve somatic growth parameters in Aim 1 patients.

**Specific Aim 2:** To assess the efficacy of 6 months of therapy with enteral GLN on somatic growth parameters [length velocity (primary endpoint), weight velocity, mid arm circumference and head circumference] in Aim 1 subjects and the impact of BSI on these growth parameters.

**The primary outcome for specific aim #2 is length velocity.** Secondary outcomes are growth parameters of weight mid arm circumference and head circumference velocities. These are clinically relevant growth parameters identified by our preliminary data in which SBS children had growth delay with short lengths and smaller head circumferences than infants without NEC or SBS.

**Data collection:** During CNC/clinic visits (baseline, days 30, 60, 90, 120, 150 and 180) as described above, each child will have weight, length mid arm circumference and head circumference measured in duplicate. These measurements will be done by a trained member of the study staff at each center. The individual at each site will be trained to perform these

measurements according to standard methods previously described. Institutional scales, length boards and measuring tapes will be used at each center.

**Expected results:** We expect that SBS children on enteral GLN supplementation will have more rapid growth as measured by the parameters above. The group with no BSI or decreased BSI (2 episodes) during the study period is expected to have a greater increase in growth parameters compared to the group with > 2 BSI.

**Hypothesis 3:** The gut luminal microbiome is altered in pediatric SBS versus non-SBS controls, correlates with BSI and is altered by enteral GLN supplementation.

**Specific Aim 3:** To comprehensively assess the gut luminal microbiome (using state-of-the art molecular methods) in Aim 1 SBS patients versus non-SBS, age-matched control subjects (primary endpoint), to correlate major bacterial dynamics present in the lumen with BSI due to specific microbes and to explore whether the gut luminal microbiome is altered by enteral GLN treatment.

**Primary outcome:** Increased *K. pneumonia* and *E. faecalis* in the gut microbiome of SBS infants with BSI.

**Secondary outcome:** Alteration in other commensals in the gut luminal microbiome of SBS infants.

**Subjects:** Infants recruited in specific aim 1 (n=48 – subjects- 36; controls- 12) Healthy age matched infants (n=12) will be recruited from the Gastroenterology and surgery clinics.

**Sample Procurement:** Stool samples (~500 mcg), will be obtained from infants' diapers or ostomy bags. Stool specimens will be collected prospectively during visits at baseline, days 30, 60, 90, 120, 150 and 180. **Stool will also be collected whenever the patient has a BSI.**

The controls (12 healthy infants) will have serial stools collected on 4 occasions, each separated by 60 days (baseline, days 60, 120 and 180).

It is anticipated that stool samples will be collected during the clinic visit. All stool samples will be scooped into a stool container and stored immediately in a -80°C freezer. For samples collected at home, subjects will be instructed to collect in a container containing RNAlater tissue reagent. This will be stored in a cold at home and when delivered to the study team will be stored in -80°C freezer until processed. RNAlater provides immediate stabilization of DNA, RNA, and protein in samples at room temperature. This preserves the in vivo profile of DNA, RNA, and proteins, allowing reliable downstream analysis. Stabilized samples can be transported at 15–25°C for up to 7 days, or stored at 2–8°C for up to 12 months. For longer storage, stabilized samples can be archived at –80°C.

**Small bowel fluid and tissue procurement:** If the patient is scheduled for a clinically indicated gastrointestinal endoscopic procedure; duodenal fluid (~1 ml) will be aspirated and an additional duodenal biopsies will be collected. Specimens will then be stored at -80°C within 10 minutes of obtaining until processing. They will subsequently be sent for bacterial composition evaluation at the University of Colorado using pyrosequencing techniques described below.

**Genomic DNA Preparation:** Total genomic DNA will be prepared from specimens using a robust protocol that entails chemical and mechanical disruption of cells, which is performed in a HEPA-filtered, UV-sterilized PCR hood. Sham extractions are performed in parallel to detect contaminated reagents. **Broad-Range PCR:** DNA lysates are subjected to PCR with pan-bacterial 16S rDNA primers (27FYM+3 and 338R), yielding libraries of PCR amplicons representative of all bacteria in a specimen. Triplicate PCR reactions will be performed and amplicons pooled for each sample. To alleviate representational bias in PCR amplicon libraries, we will determine empirically the minimum number of PCR cycles required to generate the quantities of DNA required for direct sequencing by broad-range rDNA Q-PCR. **High throughput DNA Pyrosequencing:** Subject PCR amplicon libraries will be sequenced using the high-throughput Genome Sequencer™ FLX pyrosequencing platform of Roche/454 Life Sciences, Inc., available through the University of Colorado's Consortium for Comparative Genomics. Barcoded PCR primers will be used to multiplex ~200 libraries per pyrosequencer run. Approximately 5000 rRNA gene sequences will be determined for each sample library, which based on our preliminary studies will comprise a comprehensive census of the resident microbes. Additional sequences will be screened if coverage is less than 95%.

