## IX. Methods

### A. Subjects and controls Selection

#### Inclusion criteria for age matched controls (n=12: 6 per site)

- Males and females will be recruited as controls for this study if they are  $\leq 12$  months of age (corrected for gestational age)
- Normal small bowel length without any intestinal resection or primary intestinal disease
- Not currently on TPN and if ever on TPN this should have been discontinued for at least 4 weeks

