#### G. Patient Recruitment and Consenting Process

##### Patient Recruitment

A total of 36 patients with short bowel syndrome (SBS)  $\leq$  12 months of age will be recruited for this study. Of the 36 patients, approximately 24 patients will have colon in continuity and 12 will have colon not in continuity. Assuming a 10% dropout rate, it is expected that 32 SBS patients will complete the study.

For Aim 3 of the study, an additional 12 infants without SBS will be enrolled as the non-SBS control patients. Therefore, a total of 48 patients will be enrolled across the two sites, University of Michigan and Cincinnati Children's Hospital Medical Center.

The study will be explained in detail by the study coordinator or other study team member and the consent form will be reviewed per institutional IRB requirements. These subjects will be recruited through the Division of Gastroenterology, Hepatology, and Nutrition, the Department of Surgery, or the Division of Neonatology. The prospective patients will be identified through the clinical staff within all three divisions working collaboratively. The clinical staff will initially inform potential subjects and families about the research study. The research staff will notify and obtain permission from the patient's primary gastroenterologist, surgeon, or neonatologist before contacting the family.

Subjects who drop out prior to drug initiation may be replaced with new subjects until target enrollment is achieved, as these will not have been given study medication.

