- 8) Intestinal microbial groups (e.g., species, genera) will be correlated with the treatment or control arms of the GLN supplementation trial and with bacteria identified during any diagnosed BSI. The frequency of rRNA sequences will be interpreted as the relative abundances of organisms in samples of stool and standardized by gram of stool weight. Bacteria present in specimens will be preliminarily identified by use of the Naïve Bayesian Classifier Tool of the Ribosomal Database Project. The strength of association of individual microbial groups with treatment arms and/or main outcome measures will be measured by comparing the abundances of these groups using the non-parametric Kruskal-Wallis test. Experimental reproducibility and inter- and intra-individual similarities in microbial populations will be assessed by calculating and comparing the sequence-abundance-based Morisita-Horn index. In all statistical analyses 2-sided *p*-values less than 0.05 will be considered statistically significant. Results will be corroborated through the phylogeny-based UniFrac metric, which assesses population-wide differences in microbial lineages between different groups of subjects (SBS vs. control). Stool-associated bacteria collected at BSI incidence will be compared to the species identified on blood culture to determine whether intestinal bacteria are potential sources for BSI. Alternatively, absence of particular species from the stool at the time of BSI diagnosis will indicate that lack of specific bacterial species from the stool predisposes to BSI. Tissue samples collected during endoscopy or surgery and intestinal fluid aspirated during endoscopy will be analyzed in parallel with stool samples in order to assess the use of stool samples as proxies for intestinal samples. Patterns will also be reviewed to assess for relationships to enteral feeding rate.

These methods have been used and demonstrated in 2 published studies by one of the collaborators/co-investigators.

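### Aim 3 compares SBS infants with controls without separating SBS infants by colon continuity, so a difference in sampling site could be read as an effect of SBS, or could hide one

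*Combined protocol and SAP*

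**What the plan says.** - **Specimens.** Section X, Specific Aim 3 (Sample Procurement) takes stool from "diapers or ostomy bags" and makes no later distinction between the two.
- **SBS anatomy.** Patient Recruitment expects that "approximately 24 patients will have colon in continuity and 12 will have colon not in continuity".
- **Controls.** The 12 controls must have "Normal small bowel length without any intestinal resection or primary intestinal disease".
- **Status of the comparison.** Specific Aim 3 sets SBS patients "versus non-SBS, age-matched control subjects (primary endpoint". The same section then names a primary outcome within SBS infants: more *K. pneumoniae* and *E. faecalis* in those with BSI.
- **Analysis.** Section XIII, Aim 3, measures association by "comparing the abundances of these groups using the non-parametric Kruskal-Wallis test". It corroborates with UniFrac, "which assesses population-wide differences in microbial lineages between different groups of subjects (SBS vs. control". Neither uses colon continuity or ostomy status.
- **The same variable elsewhere.** Randomization is stratified by site and colon in continuity. Ostomy status is a covariate in the Aim 1 secondary models for cytokines, sIgA, plasma glutamine and enteral share of nutrition, and in the Aim 2 growth models.
- **Nearest safeguard.** Endoscopic and surgical specimens are to be analysed in parallel with stool "in order to assess the use of stool samples as proxies for intestinal samples".

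**The concern.** In an infant whose colon is not in continuity, output collected from an ostomy bag has not passed through the colon. Control stool has. A taxon whose abundance depends on that passage will differ between the pooled SBS group and controls even if SBS itself changes nothing. A site difference in the opposite direction can cancel a real SBS difference.

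The stratified randomization does not help here. It balances glutamine against placebo within SBS, but controls are not randomized. The stool-as-proxy check does not help either: endoscopy is done only when clinically indicated, and no intestinal specimens are planned in controls.

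The within-SBS question has a related weakness. If infants without colon continuity also have a different BSI rate, the association of named species with BSI mixes infection risk with sampling site. The plan also reads the absence of a species from stool at the time of BSI as evidence of predisposition, and sampling site alone could produce such an absence. The pilot is meant to supply effect sizes for a definitive study, so a distorted estimate would carry forward.

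**Working it through.** **1. The plan's own figures.** Continuity split: 24 + 12 = 36, and 12/36 = 33.3% not in continuity. Expected share in controls: 0/12. Completers: 36 × 0.90 = 32.4, stated as 32, or about 21 and 11 on the same split. There is no sample size or power statement for Aim 3 to reproduce; those in the Sample size section concern BSI and cytokines only.

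**2. How the mixture moves a rank test.** Let d be the true SBS effect and δ the site shift in the 12 infants, both in SD units, with normal values of unit SD. A two-group Kruskal-Wallis test responds to

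P(SBS value > control value) = (24/36)·Φ(d/√2) + (12/36)·Φ((d+δ)/√2), which is 0.500 under no difference.

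With d = 0:
- δ = 1: 0.667 × 0.500 + 0.333 × 0.760 = 0.587
- δ = 2: 0.667 × 0.500 + 0.333 × 0.921 = 0.640
- δ = 3: 0.667 × 0.500 + 0.333 × 0.983 = 0.661

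The probability leaves 0.500 with no SBS effect at all. It cannot exceed 0.667, because two thirds of the SBS group is unshifted.

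**3. Rejection rates with no SBS effect.** Simulation, 20,000 runs per setting, one value per infant, 12 controls, Kruskal-Wallis at two-sided 0.05. The shifts are assumed, since the documents give none.

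| Site shift (SD) | Pooled, 24+12 v 12 | Completers, 21+11 v 12 | Colon in continuity only, 24 v 12 |
|---|---|---|---|
| 0 | 5.1% | 4.8% | 5.0% |
| 1 | 12.9% | 12.6% | 5.0% |
| 2 | 26.5% | 27.1% | 5.1% |
| 3 | 34.4% | 35.0% | 4.9% |

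**4. Masking.** Take d = 1 and δ = −2. The probability in step 2 is 0.667 × 0.760 + 0.333 × 0.240 = 0.587, against 0.760 with no site shift. Simulated pooled power falls from 81% to 8%.

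**5. Price of a like-for-like comparison.** Power with no site shift:

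| True SBS effect (SD) | 36 v 12 | 24 v 12 |
|---|---|---|
| 0.8 | 62% | 56% |
| 1.0 | 81% | 76% |
| 1.2 | 93% | 89% |

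**The case against.** Several points on the other side stand.

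- **Sample source is largely recoverable.** A reader might infer that it is lost. The documents do not support that: dates and types of surgery are collected, history is taken at each visit, presence of the colon is reviewed from surgical records, continuity is a randomization stratum, and ostomy status is a planned covariate. The gap is that Aim 3 does not use the information.
- **The abundance test is not tied expressly to SBS versus control.** Section XIII links Kruskal-Wallis to treatment arms and to the main outcome measures, and names SBS versus control only for UniFrac. The simulation assumes that the same test serves the SBS-control comparison.
- **SBS versus control is not the only candidate primary.** The within-SBS outcome competes with it, and restricting the SBS-control comparison does nothing for that outcome.
- **Small-bowel effluent is an inference.** The documents state no stoma level and no count of bag samples. They do not equate colon not in continuity with having an ostomy, and status may change over six months.
- **Lost continuity may be part of SBS.** Making the colon-in-continuity infants the sole primary set would change the target population and drop a third of it. That is a reason to show the groups side by side; it does not justify pooling alone.

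Two further extensions are tempting and do not hold. For stool sIgA, the planned contrast is glutamine against placebo, stratified by continuity and adjusted for baseline value and ostomy status, with no planned test against controls. For change over time, Aim 3 plans no formal test of microbiome change, only within-infant similarity by the Morisita-Horn index.

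**Conclusion.** The point holds as a gap in the Aim 3 analysis. Sampling site is partly confounded with group by design, about one third against none, and the SBS-control comparison has nothing to separate them. A reported difference could be due to site, and a real one could be concealed.

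The mechanism follows from the documents plus one direct anatomical inference. Its size does not. A reader might take 13% to 34% as this trial's false-positive rate; that is not supported. Those figures rest on assumed shifts of 1 to 3 SD, the planned 24/12 split, all 12 infants without continuity giving shifted samples, and one normal value per infant. The trial will collect seven scheduled samples per SBS infant and four per control. Repeated sampling does not remove the confounding, but the rates would differ. This is an inexpensive improvement to an exploratory aim, and it does not touch the BSI comparison between the randomized arms.

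**What to change.** In Section XIII, Aim 3:

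1. Report SBS versus control by colon continuity at the time of sampling: infants with colon in continuity against controls (about 24 v 12), the not-in-continuity group beside them, and the pooled result. Apply this to both the abundance tests and UniFrac.
2. Attribute a difference to SBS only if it is present in the colon-in-continuity comparison. Describe one seen only in the pooled or not-in-continuity results as possibly due to sampling site.
3. Stratify the within-SBS analyses by the same variable, including *K. pneumoniae* and *E. faecalis* with BSI.
4. Log each specimen as diaper or ostomy at collection, or state how source will be derived from the surgery dates already recorded.

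The cost is one specimen-log field or a derivation rule, and extra rows in the tables. No new samples or visits are needed. The like-for-like comparison rests on about 24 rather than 36 SBS infants, with the power loss shown above (about 5 percentage points at 1 SD), and the pooled result stays available.

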**During a BSI** the following procedure will be done: stool collection for bacterial analysis and sIgA measurement. Extra 2 ml of blood will be collected for flagellin and LPS specific IgG levels. The blood will be obtained as soon as possible when the patient is being investigated for a suspected CA-BSI. In the event that the episode does not meet the criteria for a CA-BSI the samples will not be evaluated.

All bacterial isolates obtained during the study from patients will be saved at their respective institutions (CCHMC and University of Michigan) until the end of the study in the event further work with them is required.

**Plasma glutamine analysis:** Plasma GLN will be performed using quantitative ion exchange chromatography.

**Proinflammatory cytokine evaluation:** Analysis will be performed utilizing Luminex xMAP technology (Austin TX) as previously described.

**Measurement of Flagellin and Lipopolysaccharide- specific Immunoglobulin G level:** This will be done using enzyme-linked immunosorbent assay (ELISA) as previously described.

**Safety evaluation:** The study coordinator will contact the family by phone to assess for the development of any serious adverse events on days 15(±7 days), 45 (±7 days), 75 (±7 days), 105 (±7 days), 135 (±7 days) and 165 (±7 days). There will be a 7 day grace period before and after the desired date of safety evaluation phone calls. The phone interview will assess safety and evaluate for any symptoms suggestive of adverse side effects related to L-GLN. If hospitalized, the safety evaluation will occur with the primary caregiver (bedside nurse or parent).

**Additional safety precautions:** If while enrolled in the study the patient develops multiorgan failure or requires vasopressors, the study drug will not be administered.

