**Study procedures of control group:**

Healthy age-matched infants (n=12; 6 at each site) will have serial stools collected on 4 occasions, each separated by 60 days [baseline, days 60(±15), 120(±15) and 180(±15)]. This is abbreviated compared to the study subjects.

A week prior to the scheduled date of stool collection, families will receive a brief medical questionnaire and stool container. They will be instructed to complete the questionnaire and send in with the stool specimen.

They will be provided with a sterile container with instructions to collect stool and bring in to the clinic for storage and analysis. They will be asked to collect stool on the day of the next anticipated clinic visit, put the stool in a sterile container (which may contain RNAlater) which will be supplied to them by the study team. They will put this in a storage bag, keep cool and bring the sample to the clinic visit.

Parents/Primary caregivers drop off stool specimen to the research team at the study site or will arrange with the team for the specimen to be collected from their homes.

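### The Aim 3 analysis neither excludes BSI-triggered stools from the SBS-versus-control tests nor accounts for several stools per infant

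*Combined protocol and SAP*

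**What the plan says.** **SBS infants.** Section X, Specific Aim 3, Sample Procurement: "Stool specimens will be collected prospectively during visits at baseline, days 30, 60, 90, 120, 150 and 180". The next sentence reads "Stool will also be collected whenever the patient has a BSI". The Study Procedures (Section IX.H) also call for stool during a BSI and then limit which samples are used: "In the event that the episode does not meet the criteria for a CA-BSI the samples will not be evaluated".

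**Controls.** Section IX.H, control group, says they "will have serial stools collected on 4 occasions, each separated by 60 days", and adds: "This is abbreviated compared to the study subjects". Section X repeats the four days. The numbers are given as "n=48 – subjects- 36; controls- 12".

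**Analysis.** Section X attaches the primary-endpoint label to SBS versus control in the statement of Aim 3. The primary outcome listed below it is instead an increase of two named species in SBS infants with BSI. Section XIII, item 8, tests abundances by Kruskal-Wallis at two-sided 0.05 and corroborates with UniFrac, "which assesses population-wide differences in microbial lineages between different groups of subjects (SBS vs. control". It gives stool taken at BSI one explicit use, comparison with the blood-culture species. For the SBS-versus-control tests it names no eligible stools, no time points, no unit of analysis and no method for repeated stools.

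**The concern.** A BSI-triggered stool is taken because the infant is acutely infected, and no control can supply an equivalent. The sponsor's own hypothesis is that the microbiome correlates with BSI, and the listed primary outcome expects *Klebsiella pneumoniae* and *Enterococcus faecalis* to be raised in SBS infants with BSI. If that is right, admitting BSI stools pushes the SBS-versus-control contrast for those species in a known direction, whether or not SBS itself has an effect. Infants with several BSI also contribute more stools and so count for more.

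Separately, each infant gives several stools. Kruskal-Wallis treats its observations as independent. If stools are entered one by one, the test acts as if there were far more information than 36 and 12 infants supply.

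Two analysts following item 8 could choose different sets of stools and reach different answers on the contrast that Section X labels primary.

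**Working it through.** **The plan's own figure.** Aim 3 has no sample size or power statement to reproduce. The Aim 1 statement (Section XIII, Sample size: 16 per group, 75% versus 30%, Fisher's exact test, one-sided 10%, at least 85% power) reproduces at 85.7% by exact enumeration. This point does not affect it.

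**Scheduled stools**, from the two schedules with 36 SBS infants and 12 controls:
- SBS: 36 × 7 = 252. Controls: 12 × 4 = 48.
- Days both groups share (0, 60, 120, 180): 36 × 4 = 144 against 48.
- SBS stools on days 30, 90 and 150: 36 × 3 = 108.
- Mean scheduled day: 90 in both groups.

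**BSI-triggered stools.** The plan gives no number, so this is an assumed range.
- Low: one stool per infant with a BSI at the Sample size rates, which are shares of infants with at least one BSI. 18 × 0.75 + 18 × 0.30 = 18.9, about 19. Share of SBS stools: 18.9 / (252 + 18.9) = 7.0%.
- High: the Background rate of 7.8 per 1000 catheter days, with all 36 infants on a line for 180 days and one stool per episode. 0.0078 × 180 × 36 = 50.5. Share: 50.5 / (252 + 50.5) = 16.7%.

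**Effect of admitting BSI stools.** Simulated Kruskal-Wallis at nominal 5%, 36 versus 12 infants, no true SBS effect, normal data. The 1 SD shift of BSI stools is an assumption.

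| Stools used | No BSI stools | About 19 | About 50 |
|---|---|---|---|
| Pooled, no within-infant correlation | about 5% | 6–7% | 15% |
| One mean per infant, correlation 0.3 | about 5% | 6% | 11% |

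With a shift of 0.5 SD, the pooled figures are 5% with 19 BSI stools and 7% with 50. The second row shows that one mean per infant does not remove the effect while BSI stools stay in.

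**Effect of repeated stools**, scheduled stools only, at assumed within-infant correlations:

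| Analysis | 0.3 | 0.5 | 0.7 |
|---|---|---|---|
| 7 v 4 stools, pooled as independent | 16% | 23% | 29% |
| 4 v 4 matched stools, pooled as independent | 15% | 20% | 27% |
| One mean per infant, 7 v 4 | 5% | 5% | 5% |
| One mean per infant, 4 v 4 | 5% | 5% | 4–5% |

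Matching visits while still pooling barely helps. One mean per infant restores about 5% on either schedule. With no within-infant correlation, the 7 v 4 per-infant mean gave 7%; there the two groups' means differ in precision but not in expected value.

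**The case against.** The strongest reply is that the plan never says BSI stools enter the SBS-versus-control comparison. Item 8 gives them a separate use, the UniFrac sentence speaks of groups of subjects, and stools from episodes that fail the infection criteria are not evaluated. This stands in part. A reader might infer that the comparison includes these stools, and the documents do not say so. But the blood-culture use is not made exclusive, and the abundance test carries no restriction. The stools that are evaluated are, by the plan's own rule, those from confirmed infection.

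A second reply is that unequal sampling frequency is not an error. This stands. The shorter control schedule is declared, every control day is also an SBS day, and the mean scheduled day is the same, so under a common linear age trend the spacing alone does not bias the comparison. A reader might add the two kinds of unmatched stool and report that about half of SBS stools lack a control counterpart: (108 + 18.9) / 270.9 = 47%, up to (108 + 50.5) / 302.5 = 52%. That total is not a measure of bias, because 108 of those stools are routine visits.

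A reader might also argue that more stools favour finding a taxon at least once in SBS. Item 8 compares abundances and plans no such ever-detected analysis.

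Finally, the high count of BSI stools ignores the assumed 10% dropout and any weaning from parenteral nutrition, so it is an upper figure under that rate. The low count ignores repeat episodes.

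**Conclusion.** The point holds as an omission with a foreseeable bias. Section XIII, item 8, leaves BSI-triggered stools eligible for a contrast in which controls can have none, and it gives no rule for several stools per infant. BSI stools would be about 7% to 17% of SBS stools. If they differ by 1 SD, admitting them raises false positives from about 5% to 6–15% when stools are pooled, or 6–11% with one mean per infant at correlation 0.3. Pooling repeated stools as independent is the larger risk, at 16–29% for correlations of 0.3 to 0.7. The shift and the correlations are assumptions; the documents give neither.

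The documents do not support the stronger claims that the comparison is planned to include BSI stools, or that the 252-versus-48 imbalance is itself a bias. The plan should be changed before analysis. Aim 1 is untouched.

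**What to change.** In Section XIII, item 8, state that:

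1. BSI-triggered stools are excluded from every SBS-versus-control test, including UniFrac.
2. These tests use scheduled stools only, with one summary per infant, which keeps Kruskal-Wallis usable. The alternative is a model with a random infant effect and visit. Visit cannot be a factor in a one-way Kruskal-Wallis test.
3. Days 0, 60, 120 and 180 (144 versus 48 stools) are either the matched primary set or a sensitivity analysis, with the choice fixed in advance.
4. BSI stools are kept for within-SBS analyses: the blood-culture comparison already planned, plus a paired comparison with the same infant's last scheduled stool before the BSI.

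The cost is SAP wording and a little more analysis work. No visits or samples are added. The control contrast loses the BSI stools. If the four shared days are made primary, it also loses 108 of 252 scheduled SBS stools (43%), which remain available for within-SBS analyses. Using the shared days as a sensitivity analysis avoids that second loss.
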